5.8 Restrictions

5.8.1 Prior Therapy

Subjects must discontinue the use of any of the therapies or interventions listed in Table 1 for the specified period prior to the Screening visit:

Aerie Pharmaceuticals, Inc.

Table 1 Required Washout for Prohibited Therapies or Interventions Prior to the Screening or Baseline Visit

| Treatment/Intervention | Washout Required Prior to the Screening Visit |
|--|--|
| Artificial tears | 2 hours |
| Contact lenses | 7 days |
| Punctal or intracanalicular plugs | 1 year |
| Regular use of topical ocular medications (including ocular cyclosporine or other prescription ophthalmic solution for DED (e.g., Restasis®, Cequa™, Xiidra®), topical ocular corticosteroid- or non-steroidal-anti-inflammatory agents, glaucoma medications eye whitening products (e.g., Visine®, Lumify®) topical antibiotics, topical anti-histamines, mast cell stabilizers or other OTC, herbal, prescription, or nutritional supplements). Note: Occasional (as needed) > 24 hours prior to the Screening Visit may be permitted | 30 days |
| Lid-heating therapy, Meibomian gland probing, or therapeutic Meibomian gland expression | 1 year |
| TrueTear® | 45 days |
| Regular use of lid hygiene | 14 days |
| Any systemic medication known to cause ocular drying (e.g. antihistamines, antidepressants, beta-blockers) started < 14 days prior to the Screening visit or a change in dosage is anticipated during the study. Note: Occasional (as needed) use of medications such as systemic antihistamines will be permitted | 14 days ^a |
| Treatment/Intervention | Washout Required Prior to the Baseline Visit |
| Medications associated with the treatment of severe DED and/or Meibomian gland disease such as oral pilocarpine, oral cevimeline, oral macrolides, oral tetracyclines, oral tetracycline derivatives, and oral retinoids | 90 days |
| Systemic immunomodulators (e.g., hydroxychloroquine, methotrexate, cyclosporine) started < 90 days prior to the Baseline Visit or a change in dosage is anticipated during the study | 90 days ^b |
| Systemic corticosteroids (IV and oral) started < 90 days prior to the Baseline Visit or a change in dosage is anticipated during the study | 90 days ^b |

- a. The use of these therapies is allowed during the study provided that the dosing regimen is stable for at least 14 days prior to the Screening visit and does not change at any time during the study duration. The total time for washout if one of the systemic medications known to cause ocular dryness was stopped is 14 days relative to Screening visit.
- b. The use of these therapies is allowed during the study provided that the dosing regimen is stable for at least 90 days prior to the Baseline Visit and does not change at any time during the study duration. The total time for washout if one of these medications was stopped is 90 days relative to Baseline Visit

5.8.2 Fluid and Food Intake

None

5.8.3 Subject Activity Restrictions

Subjects are to administer their morning dose of randomized treatment on the days of Visits 2, 3, 4 and 5. Subjects are not to administer the evening dose of the randomized treatment on the days of Visits 2, 3, and 4 since it is administered during the clinic visit.

5.8.4 Females of Childbearing Potential and Acceptable Contraceptive Methods

An adult woman is considered of childbearing potential unless she is at least 1-year post-menopausal (defined as 12 consecutive months with no menses without an alternative medical cause) or 3 months post-surgical sterilization (includes hysterectomy, bilateral oophorectomy, or bilateral tubal ligation). All females of childbearing potential must have a negative urine pregnancy test result at the Screening, Baseline and Exit Visits. Pregnancy tests must be negative for the subject to receive study intervention. Subject must not intend to become pregnant during the study and must properly use a reliable method of contraception. The following methods of contraception are considered reliable: hormonal contraceptives, intrauterine device, surgical sterilization, partner with vasectomy, or sexual abstinence. For male subjects in the study, condoms are considered a reliable method of contraception.

If pregnancy occurs during the study, every attempt will be made to collect data on the pregnancy of female subjects. Signature of a separate consent form will be requested of the pregnant woman. Information on pregnant partners of study subjects will not be collected.

Every attempt will be made to collect data regarding the newborn child born to a female subject with parent/guardian permission. One parent or the legal guardian will be requested to provide permission for the minor to participate in this part of the research.

5.9 Permitted Interventions

Therapy considered necessary for the subject's welfare may be given at the discretion of the investigator. If the use of a specific therapy or intervention is in question, please contact Aerie.

Use of the following is permitted during the study:

- Any systemic medication not itemized as an exclusion in Section 4.3 is permitted.
- Occasional (as needed) use of medications such as non-prescription antiinflammatories / pain relievers (e.g. aspirin, acetaminophen etc.), and acidreflux/heartburn medications will be permitted.
- Occasional (as needed) use of and cold/flu medications that **do not** contain antihistamines will be permitted. Cold/flu medications that **do** contain antihistamines are discouraged but will be permitted (please refer to the Allowed Concomitant Medication List).
- Skin care products containing retinoids are permitted.

Any medication taken during the study between the date of the first dose of randomized study treatment and the date of the Exit visit or Early Termination visit should be recorded in the case report form (CRF) as a concomitant medication.

5.10 Treatment Compliance

For Visit 1, the morning dose will be administered in clinic by the subject under supervision from site personnel. For Visits 2, 3 and 4, the second dose will be administered by designated site personnel; all other doses will be administered by the subject.

In-between office visits, study compliance will be monitored by counting the number of used and unused vials dispensed and returned. Subjects will be instructed on instillation and storage of study treatment at the end of Visits 1, 2, 3, and 4, as well as provided written instructions. The subject's used and unused study treatment vials will be collected at each visit from Visit 2 up to and including Visit 5 to assess dosing compliance. Dosing compliance will be based off the used and unused vial count. If the subject is less than 80% or more than 125% compliant with dosing based on the expected number of used and unused vials, then the subject will be deemed non-compliant and a deviation should be recorded.

These guidelines will be used by the Investigator for determining the subject's necessary compliance for the study and for recording deviations from this compliance.

The study centers will keep an accurate accountability record that specifies the amount of study treatment dispensed to each subject, the amount of study treatment returned to the site, and the dates of each.

5.11 Packaging and Labeling

Each packaged unit will be labeled with an investigational label with the information required per applicable regulations.

The products for each individual treatment assignment will be packaged into identical subject kits; each subject kit will contain one of 3 treatments: AR-15512 ophthalmic solution 0.0014%, 0.003% or AR-15512 ophthalmic solution, vehicle.

5.12 Storage and Accountability

The study treatment must be dispensed or administered according to the procedures prescribed in this protocol and Pharmacy Manual. Only qualified subjects may receive study treatment, in accordance with all the applicable regulatory requirements. Only authorized staff is allowed to dispense these treatments. Under normal conditions of handling and administration, the study treatments are not expected to pose significant safety risk to site staff. Adequate precautions must be taken to avoid direct contact with the study treatment. The study treatments will be stored in a secure area under the appropriate physical conditions for the product. Access to the study treatment will be limited to authorized site staff only. The study treatments will be stored as directed on the investigational label. The study treatments should be stored in clinic refrigerated (2°C to 8°C/36°F to 46°F) until dispensed to the subject. Temperature of the study treatment storage location at the site is to be monitored using a calibrated monitoring device and documented. At time of dispensing, the subject will be instructed to store the study treatment per details in the Pharmacy Manual and to protect from light (store in carton) as directed on the investigational label. Subjects should be instructed not to freeze the study treatment.

5.12.1 Receipt and Disposition of Study Medication

Study treatments will be shipped to the Investigator's site from a central depot. A study staff member at the Investigator's site who is not involved in conducting any efficacy or safety procedures will verify study treatment shipment records by comparing the shipping documentation accompanying the study treatment to the study treatment actually received at the Investigator's site. If a discrepancy is noted, the appropriate individual at the Sponsor or designee must be notified immediately, in accordance with the Pharmacy Manual. The responsible person(s) for dispensing study treatment at the Investigator's site is the only site staff member permitted to distribute investigational product and also has sole responsibility to account for all returned used, partially used and unused vials and kits of study treatment. The study treatment(s) must not be used outside this protocol. An Investigational Product Accountability Log will be kept at each clinical site.

5.12.2 Return of Study Medication

When the study is completed or is terminated by the Sponsor, all study materials including used and unused study treatment kits / vials will be returned to the Sponsor or their designee. Subjects should be instructed to retain all vials (used, partially used or unused) of study treatment and return them to the clinical site. All study treatment accounting procedures must be completed before the study is considered to be concluded. The responsible person(s) at the Investigator's site has the sole responsibility to account for all used, partially used, and unused study treatment. This site staff member at the Investigator's site will complete a study treatment returns form or equivalent that will be signed by the Investigator or designee prior to returning the used and unused study treatment kits /vials to the Sponsor or their designee.

6. STUDY PROCEDURES

6.1 Informed Consent

Prior to any study procedures, the study will be discussed with each subject, and subjects wishing to participate must give written informed consent. The verbal explanation of the study will cover all the elements specified in the written information provided for the subject. The Investigator will inform the subject of the aims, methods, anticipated benefits, and potential hazards of the study, including any discomfort it may entail. The subject must be given every opportunity to clarify any points he/she does not understand and, if necessary, may ask for more information. At the end of the interview, the subject should be given time to reflect. Subjects and/or a legally authorized representative then will be required to sign and date the ICF.

The ICF must have received approval/favorable review by a properly constituted Institutional Review Board (IRB) prior to use. A copy of the signed and dated consent document will be given to each subject. The original signed and dated ICF must be maintained in the study files at the Investigator's site.

The Investigator or staff is responsible for ensuring that no subject is exposed to any study related examination or activity before the subject has given written informed consent. It should be emphasized that the subject is at liberty to withdraw consent to participate at any time, without penalty or loss of benefits to which the subject is otherwise entitled. Subjects who refuse to give, or withdraw, written informed consent may not be included or continued in this study, and should be notified that discontinuation from the study will not impact their subsequent care.

6.2 Demographics and Medical History

Demographic data and any ongoing medication use will be collected and recorded. Significant medical and ophthalmic history will be collected and any current underlying medical/ophthalmic conditions, including those that may have resolved before the Screening Visit, must also be recorded.

6.3 Vital Signs

Systolic and diastolic blood pressure will be measured using an appropriate sphygmomanometer after subjects have been at rest (seated) for at least 5 minutes. Blood pressure will be recorded in mmHg.

Heart rate will be measured using manual or automated methods in beats per minute (bpm) after the subject has been in a resting state (seated) for at least 5 minutes. If measured manually, pulse will be counted for 30 seconds, multiplied by 2, and recorded in bpm.

6.4 Clinical Laboratory Tests

6.4.1 Laboratory Parameters

A chemistry panel, a complete blood count (hematology and differential), and urinalysis will be performed as described in the Laboratory Manual.

The clinical laboratory results must be reviewed by the Investigator prior to subject enrollment, and the tests cannot be indicative of any clinically significant or uncontrolled disease in the opinion of the Investigator.

6.4.2 Pregnancy Testing

Urine pregnancy tests for women of childbearing potential (WOCBP; defined in Section 5.8.4) are required at Screening, Baseline and Exit Visits. Pregnancy tests must be negative for the subject to receive study treatment.

6.4.3 Sample Collection, Storage and Shipping

The site staff responsible for collecting the laboratory samples will be identified on the Site Authorization and Delegation Log. Details for the preparation and shipment of samples and reference ranges will be provided in the Laboratory Manual.

6.5 Dispensing Investigational Product

Study-related site personnel will be cautioned that any used or unused study treatment kits are not to be opened at the clinical site by the site staff involved in efficacy or safety assessments.

Study staff responsible for dispensing study treatment will be listed on the Site Authorization and Delegation Log. When a subject meets all criteria for enrollment, the subject will be randomly assigned to a study treatment according to the IWRS. The responsible study staff will account for all used, partially used and unused study kits / vials by maintaining an Investigational Product Accountability log.

Details of timing and procedures for dispensing Investigational Product are found in the Pharmacy Manual.

6.6 Efficacy Assessments

6.6.1 Symptom Questionnaire (Visual Analog Scale (VAS))

Subjects will be asked to rate each of the following DED symptoms (both eyes together), over the last 24 hours (pre-CAE) and "now/currently" (post-CAE), each on a separate VAS: ocular discomfort (ODS), eye dryness (EDS), ocular pain (OP). For each VAS, subjects will be asked to place a vertical mark on the horizontal line to indicate the level of each symptom, with 0 corresponding to "no symptom" and 100 corresponding to "maximal symptom". The assessment line length of the scale will be 100 mm and will be similar to the following depiction for ocular discomfort (Figure 3).

While in the CAE, subjects will be reassessed at 5-minute intervals on only the ODS-VAS based on how they feel "now/currently".

Figure 3 Ocular Discomfort: Visual Analog Scale

0 100
(No Ocular Discomfort) (Maximum Ocular Discomfort)

6.6.2 Symptom Assessment in Dry Eye (SANDE) Questionnaire

The SANDE questionnaire (Schaumberg 2007) is comprised of 2 unique VAS scales to assess the frequency and severity of DED symptoms.

The assessment line length of the scale will be 100 mm and will be similar to the following depiction (Figure 4). Higher scores indicate greater frequency or severity.

[figure not shown]
Aerie Pharmaceuticals, Inc.

[figure not shown]
The Global SANDE score will be calculated by multiplying the frequency score by the severity score and obtaining the square root. The final value must be rounded to the nearest whole number.

[figure not shown]
Figure 4 SANDE Questionnaire

PLEASE COMPLETE THE FOLLOWING QUESTIONS REGARDING THE FREQUENCY AND SEVERITY OF YOUR DRY EYE SYMPTOMS:

| 1. Frequency of sym | ptoms: | | |
|---|-----------|--|--|
| Place a single vert your eyes feel dry | | tal line to indicate how often , on average, | |
| 1. Frequency | Rarely | All the time | |
| | | tal line to indicate how severe, on average, irritation. | |
| 2. Severity | Very Mild | Very Severe | |
| | | | |

[figure not shown]

[figure not shown]

Aerie Pharmaceuticals, Inc.

6.6.6 Anesthetized Schirmer Test

[figure not shown]
The test should be performed in a room with no direct air or sunlight on the subject's face by the Investigator or designated sub-Investigator. Every effort should be made to ensure the same individual performs this assessment for a given subject at each applicable visit. Under ambient light, the subject will be instructed to look forward and to blink normally during the course of the test. Topical anesthetic drops such as 0.5% proparacaine hydrochloride or equivalent should be instilled in both eyes of the subject. The subject will be instructed to keep the eyes gently closed for 1 minute. After opening the eyes and allowing the eyes to recover for approximately 1 additional minute, excess moisture in the inferior fornix can be gently removed with a spear. Schirmer's strips will be placed in each eye at the junction of the middle and lateral thirds of the lower eye lid. Under ambient light, the subject will be instructed to look forward and to blink normally during the course of the test. The timer should be started immediately after the strips are inserted. The Schirmer's strips should remain in place until 5 minutes have elapsed or both strips have reached maximum score. After 5 minutes, strips will be removed from both eyes and the amount of wetting will be recorded. As the tear front may continue advancing a few millimeters after it has been removed from the eyes, it is important to read the tear front immediately after removal. Only whole numbers are to be recorded, rounding up to the nearest whole number if the tear front is at or greater than the half millimeter mark.

AR-15512 Ophthalmic Solution Clinical Study Protocol: AR-15512-CS201, Amendment 4 Aerie Pharmaceuticals, Inc.

AR-15512 Ophthalmic Solution Clinical Study Protocol: AR-15512-CS201, Amendment 4 Aerie Pharmaceuticals, Inc. AR-15512 Ophthalmic Solution Clinical Study Protocol: AR-15512-CS201, Amendment 4 Aerie Pharmaceuticals, Inc.

Aerie Pharmaceuticals, Inc.

Clinical Study Protocol: AR-15512-CS201, Amendment 4

6.7.2 Controlled Adverse Environment (CAE) Exposure

Subjects will be exposed to the CAE for approximately 90 minutes during each CAE visit (Visits 1, 2, and 5 as well as Visit 4 at selected sites). The ODS-VAS and Ora Calibra ODS scores will be collected upon entering the CAE and approximately every 5 minutes thereafter.

This procedure will be performed according to Ora, Inc. SOPs and/or guidance documents.

6.8 Safety Assessments

6.8.1 **Best-Corrected Visual Acuity (BCVA)**

Visual Acuity Procedures

LogMAR visual acuity must be assessed using an ETDRS Series 2000 chart. The procedure used will be consistent with the recommendations provided for using an ETDRS eye chart. Visual acuity should be evaluated at the beginning of each visit in the study (i.e., prior to slit lamp examination). Subjects should use the most recent correction to attain their BCVA; if they forget their spectacles, this prescription can be placed in a trial frame.

Equipment

An ETDRS Series 2000 visual acuity chart must be used. If smaller reproduction (18" by 18", e.g., from Prevent Blindness) wall charts are used, the subject viewing distance should be exactly 10 feet (or as specified by the manufacturer). In ALL cases, for purposes of standardizing the testing conditions during the study, all sites must use only ETDRS Series 2000 Charts and the right eye should be tested first. For reflectance (wall) charts, the chart should be placed frontally and be well illuminated.

Measurement Technique

The chart should be at a comfortable viewing angle. The right eye should be tested first. The subject should attempt to read each letter, line-by-line, left to right, beginning with line 1 at the top of the chart. The subject should be told that the chart has letters only, no numbers. If the subject reads a number, s/he should be reminded that the chart contains no numbers, and the examiner should then request a letter in lieu of the number. The subject should be

asked to read slowly, so as to achieve the best identification of each letter. S/he is not to proceed to the next letter until s/he has given a definite response.

If the subject changes a response (e.g., 'that was a "C" not an "O"') before s/he has read aloud the next letter, then the change must be accepted. If the subject changes a response having read the next letter, then the change is not accepted. The examiner should never point to the chart or to specific letters on the chart during the test.

A maximum effort should be made to identify each letter on the chart. When the subject says s/he cannot read a letter, s/he should be encouraged to guess. If the subject identifies a letter as one of two letters, s/he should be asked to choose one letter and, if necessary, to guess. When it becomes evident that no further meaningful readings can be made, despite encouragement to read or guess, the examiner should stop the test for that eye. However, all letters on the last line should be attempted as letter difficulties vary and the last may be the only one read correctly. The number of letters missed or read incorrectly should be noted.

LogMAR Visual Acuity Calculations

The last line in which a letter is read correctly will be taken as the base logMAR reading. To this value will be added the number "N x 0.02" where 'N' represents the total number of letters missed up to and including the last line read. This total sum represents the logMAR visual acuity for that eye.

Example: Subject correctly reads 4 of 5 letters on the 0.2 line, and 2 of 5 letters on the 0.1 line.

| Base logMAR | = 0.1 |
|--|--------------|
| N (total number of letters incorrect on line 0.2 as well as 0.1) | = 4 |
| N x T (T=0.02) | = 0.08 |
| Base $logMAR + (N \times T)$ | = 0.1 + 0.08 |
| logMAR visual acuity | = 0.18 |

Repeat the procedure for the left eye.

In order to provide standardized and well-controlled assessments of visual acuity during the study, all visual acuity assessments at a single site must be consistently done using the same lighting conditions and same correction if possible during the entire study. If the same correction cannot be used (i.e., a subject broke his/her glasses), the reason for the change in correction should be documented.

Note: A clinically significant visual acuity decrease (defined as an increase of 0.32 or greater in logMAR score) from the Screening Visit (Visit 1) should be evaluated by the Investigator as a potential AE.

6.8.2 Biomicroscopy and Dilated Fundus Exam by Slit Lamp

Biomicroscopy:

Slit lamp biomicroscopic observations will be graded as Normal or Abnormal. Abnormal findings will be categorized as clinically significant (findings that may interfere with study parameters or otherwise confound the data as determined by the investigator) or not clinically significant (NCS). The following will be examined:

- Cornea
- Conjunctiva
- Anterior Chamber
- Iris
- Lens
- Eyelid

External magnification and biomicroscopy will be performed using a slit-lamp. Magnification will be consistent with standard clinical practice. The subject will be seated.

Dilated Fundoscopy:

Dilated fundus exams will be performed using indirect ophthalmoscopy. The investigator will make observations of the vitreous, retina, macula, choroid and optic nerve.

Observations will be graded as Normal or Abnormal. Abnormal findings that are clinically significant (as determined by the investigator that may interfere with study parameters or otherwise confound the data) and those that are not clinically significant will be described. An indirect Fundoscopy examination should be performed if retinal disease is detected.

- Vitreous: Examination should emphasize the visual axis.
- Retina, Macula, Choroid: Include an observation of the retina and its blood vessels. Eyes should be excluded from the study if active inflammation is present.
- Optic Nerve: Significant damage or cupping to the optic nerve should be noted.

It is recommended that tropicamide 1% ophthalmic solution be used to dilate subjects.

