9. SAFETY EVALUATION

9.1 Overview of Safety Analysis Methods

All safety analyses will be carried out using the Safety Population and will include the study eye and fellow eye separately, where applicable.

The assessment of safety will be evaluated by:

- Adverse events
- Slit-lamp biomicroscopy
- Dilated fundus exam
- Best Corrected Visual Acuity (BCVA)
- Intraocular pressure (IOP)

All safety variables will be descriptively summarized by treatment group at each assessment time and for relevant changes from baseline, where applicable.

For complete inclusion of subjects who withdraw from the study early, the End of Study visit for safety outcomes will be defined as either Visit 5 (Day 84) or Early Discontinuation.

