9.6 Dilated Fundus Examination

Dilated fundus exam results at each visit will be presented in data listings. A separate listing will be created for those subjects with a criterion change, defined as a change from "Normal" to "Abnormal" or a change from "Abnormal – Not Clinically Significant" to "Abnormal – Clinically Significant."

Frequencies and percentages of normal and abnormal results will be created for the following fields: Vitreous, Retina, Macula, Choroid, and Optic Nerve. Abnormal results will further be

Version 1.0 Page 34 of 42

broken down by clinical significance and non-clinical significance. A shift from baseline in the results for study eyes and fellow eyes will also be summarized by treatment group.

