9.7 Slit-Lamp Biomicroscopy

Biomicroscopy results will be listed at each visit. A separate listing will be created for those subjects with a criterion change, defined as a change from "Normal" to "Abnormal" or a change from "Abnormal – Not Clinically Significant" to "Abnormal – Clinically Significant."

Frequencies and percentages of normal, abnormal results will be created for the following fields: Cornea, Conjunctiva, Anterior Chamber, Iris, Lens, and Lid. Abnormal results will further be broken down by clinical significance and non-clinical significance. A shift from baseline in the results for study eyes and fellow eyes will also be summarized by treatment group.

Version 1.0 Page 35 of 42

Version 1.0 Page 36 of 42

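### Slit-lamp and fundus findings are graded clinically significant by whether they disturb the data, not by their importance to the subject, so descriptive safety summaries can mislabel them

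*Protocol*

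**What the plan says.** Protocol 6.8.2 stands under Safety Assessments. For the slit lamp, each structure is graded normal or abnormal, and an abnormal finding counts as "clinically significant (findings that may interfere with study parameters or otherwise confound the data as determined by the investigator". All other abnormal findings are not clinically significant (NCS). The fundus paragraph repeats the test: "Abnormal findings that are clinically significant (as determined by the investigator that may interfere with study parameters or otherwise confound the data".

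SAP 9.1 names both exams among the measures by which safety is judged ("The assessment of safety will be evaluated by" introduces the list). SAP 9.6 and 9.7 first tabulate normal against abnormal. They then add: "Abnormal results will further be broken down by clinical significance and non-clinical significance". On listings, 9.7 says "A separate listing will be created for those subjects with a criterion change", and 9.6 gives the rule, which 9.7 shares: "defined as a change from 'Normal' to 'Abnormal' or a change from 'Abnormal – Not Clinically Significant' to 'Abnormal – Clinically Significant". Both sections also plan a shift from baseline but do not name its categories. The SAP text available does not define clinical significance, and SAP section 12 declares no departure from the protocol's analyses.

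**The concern.** The grade reported as a safety result asks an eligibility question: does the finding disturb what the study measures? That differs from whether the finding matters to the subject's eye, and the two answers can diverge in either direction. A reader of the CS/NCS table will take it as a statement about medical importance.

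Other parts of the protocol suggest that a limb is missing here. Exclusion criteria 1 and 18 each set subject safety beside interference with the study. Section 6.4.1 ties clinical significance in laboratory results to disease. Section 6.8.1 sets a threshold for visual acuity loss (0.32 logMAR from Screening) and says that such a loss "should be evaluated by the Investigator as a potential AE". Section 6.8.2 has neither a subject-safety limb nor a pointer to the adverse-event rules.

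At stake are the CS/NCS split, the second listing trigger, and consistency between sites, since a site that follows the wording and a site that uses ordinary clinical judgement could grade the same finding differently.

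**Working it through.** The plan states no figure on this point, so the check compares the definition with the SAP's rules.

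**Inputs.** The definition of CS (Protocol 6.8.2, both exams); the two listing triggers and the CS/NCS split (SAP 9.6 and 9.7); exam timing (Protocol 7.1 to 7.5 and Appendix 4); the adverse-event rules (Protocol 6.9.1, 6.9.2 and 9.10).

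**Step 1. Where grade and importance part.** A finding either matters to the subject or does not, and either disturbs the data or does not. If it does both or neither, the written grade agrees with its medical importance. The other two combinations disagree:
- important but not disturbing: graded NCS;
- harmless but disturbing: graded CS.

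**Step 2. Follow these through the SAP**, for one structure in one eye.

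| Change | Grade as written | Criterion-change listing | CS/NCS breakdown |
|---|---|---|---|
| Normal to an important, non-disturbing abnormality | NCS | Listed (first trigger ignores the grade) | Shown as not significant |
| Abnormal-NCS that becomes important, still non-disturbing | Stays NCS | Not listed | Shown as not significant |
| Normal to a harmless, disturbing abnormality | CS | Listed | Shown as significant |
| Abnormal-NCS, harmless, that becomes disturbing | CS | Listed (second trigger) | Shown as significant |

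The breakdown can be wrong for any abnormal finding. Omission from the criterion-change listing occurs only in the second row.

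**Step 3. The shift table.** In the second row, a table with CS/NCS categories shows no shift because the grade has not moved; a grade based on importance would show one. A table with only normal and abnormal shows no shift under either definition. The definition therefore costs information here only if CS/NCS categories are used, and the SAP does not say.

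**Step 4. Reach.** There are 6 slit-lamp and 5 fundus structures: 6 + 5 = 11 per eye, or 11 × 2 = 22 per subject when both exams are done. These are gradings made, not gradings at risk. Only abnormal ones can carry a wrong label, and only structures already Abnormal-NCS can miss the listing. The slit lamp is used at every scheduled visit. The fundus is examined only at Screening and at Visit 5 or Early Termination. The documents give no rate of abnormal or worsening findings, so no expected count can be computed.

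**Step 5. What catches the second row elsewhere.** Protocol 6.9.1 requires every adverse event to be documented. The notes in 6.9.2 treat a change in health after treatment starts as treatment-emergent, and exempt a pre-existing condition only if it is unchanged or better. Section 9.10 counts worsening as well as new onset. None of these depends on the CS grade.

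**The case against.** The best defence is that the wording is poor but little depends on it. Most of this stands.

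- Study parameters is not defined as the Schirmer test and symptom scales. Visual acuity and intraocular pressure are also study assessments, and exclusion 2 cites macular degeneration as a disease that can affect vision. A sight-affecting fundus finding can therefore qualify as CS through visual acuity. A reader might infer that nearly all fundus abnormalities are forced into NCS; the text does not support that.
- A reader might also infer that important worsening disappears. It does not. SAP 9.6 and 9.7 list all results by visit; only the separate criterion-change listing can omit a case, and only within a structure already Abnormal-NCS. A subject with an abnormal eyelid at baseline is still flagged if a normal cornea becomes abnormal.
- The adverse-event rules require worsening to be recorded whatever the grade.
- Normal against abnormal is tabulated first, and CS/NCS is a further split. To say that the exams fail to measure safety would go too far.
- The CRF completion guide is not among the documents, so it may already instruct sites on grading.

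None of this repairs the definition. A full listing does not correct a mislabelled summary table, and the adverse-event rules do not make the CS/NCS column mean what its title says. The SAP takes the protocol's grade as it stands.

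**Conclusion.** The point holds as a defect of definition with limited reach. Followed as written, 6.8.2 lets the CS/NCS breakdown mislabel findings in both directions. It also lets worsening within a structure already Abnormal-NCS miss the criterion-change listing, and the shift table if that table uses CS/NCS categories. The damage is mislabelling in descriptive safety summaries. The primary and secondary efficacy analyses are not involved, and the documents do not support a claim that harmful findings go unrecorded.

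This assumes that investigators apply the wording literally and that no instruction outside these documents overrides it. Misclassification is possible rather than certain, and its frequency is unknown. It is worth correcting because the grade is reported as a safety result and the correction is cheap.

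**What to change.** In Protocol 6.8.2:
- define the safety grade, at all visits, by the finding's importance to the subject in the investigator's judgement, adding the subject-safety limb already present in exclusions 1 and 18;
- keep possible interference with study data as a separate eligibility judgement at Visits 1 and 2;
- cross-refer any post-randomization change to Abnormal-CS to the existing adverse-event rules, as 6.8.1 does for visual acuity.

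SAP 9.6 and 9.7 can then use the grade as it stands. They should state whether the shift tables use normal/abnormal or normal/NCS/CS.

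The cost is a few sentences in the protocol, a line in the SAP and matching CRF instructions, with no new procedure. Grades already recorded under the present wording would need a site query.
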